Title: A Communication-Based Study Focused on Assessing and Improving Hepatitis C Screening Rates, as well as Treatment Rates in Arizona as a Step Towards Disease Eradication Site Location: Liver Institute PLLC [name] United States of America To eradicate the prevalence of hepatitis C in Arizona through improving **Objective:** awareness, increasing population screening rates, and providing linkage to care. **Introduction:** The World Health Organization has set a goal of Hepatitis C (HCV) eradication by 2030 and this study's focus is to assist in accomplishing this goal. The utility of modern technology such as texting, emails, and phone calls in eradication of a communicable disease has not been studied and validated. The utilization of modern technology such as texting, emails, and phone **Hypothesis:** calls will expedite population-based HCV screening. Digital coding of these screened subjects will help to connect individuals with care. Moreover, the utility of digital technology such as telemedicine would increase the rate of HCV treatment. Taken together, modern technology will expedite the process of HCV eradication. **Research Aim:** The aim of this study is to assess the HCV screening rate in Arizona by identification of potential HCV patients/subjects through different methods of communication - text message, email, social media, radio, newspaper ads, and flyers. **Research Gaps:** Currently, patients are screened by a primary care physician based upon presentation including liver function tests, abnormal liver imaging, or disclosed high risk behavior. Although the Center for Disease Control (CDC) has recommended universal screening of "baby boomers", adherence to this recommendation is poor in the primary care setting. With the current rate of screening for HCV infection, eradication of HCV

Clinical Study Protocol Synopsis

infection by 2030 as per WHO recommendations is not an achievable timeline in the United States.

The study will focus on various methods of communication to reach the **Methods:** population of Arizona from the most prevalent counties to lowest prevalence. The study is organized into phases focusing on the various communication methods beginning with direct communication through mass text messages and mass emails followed by indirect communication through social media (YouTube, Facebook), newspaper, radio, Alcoholics Anonymous meetings, Narcotics Anonymous meetings, and homeless shelters. Each phase will consist of four cycles of a monthly intervention period in which communication will be active and a two-month gap that will be used to assess effectiveness of the communication method. Subjects will receive information on HCV, contact information for the study coordinator at the Liver Institute PLLC to address questions or concerns, and a code that will allow them to receive a free HCV screening test at their local Sonora Quest Lab. This code can be used at the time of receipt or a few months later, whenever the subject is ready for testing. This timeline allows to enhance subject compliance. The results from Sonora Quest Lab will be transmitted to the study coordinator at the Liver Institute PLLC and depending on the subject's insurance status will link the subject to a treatment center. Ideally it will be their primary care physician but if the subject does not have one then it will be the closest treatment center. Alternatively, the Liver Institute PLLC is also equipped to provide telemedicine appointments to evaluate the subject and provide treatment depending on insurance status. Those that are uninsured will be provided with available options for treatment. All subjects will receive information on the disease to reduce transmission and encourage friends/family to get tested. This study will function on a version of the test-and-treat approach to help reduce the spread of HCV in the Arizona population. **Results:** The study will allow us to obtain diagnostic rates for each communication method as well as the number of HCV positive individuals that are linked to care for treatment. By comparing diagnostic rates between communication methods, we can identify the most successful method to utilize for a bigger subject outreach. Additionally, by determining the rates of HCV positive individuals linked to care, we can identify deficits in the treatment of screened individuals. These components taken together will allow us to evaluate the overall success of our study.

Conclusion:The United States is well behind the overall goal of HCV eradication by
2030. To successfully facilitate completion of this goal, a new process of
HCV screening and linkage to treatment is necessary. We propose a study

	focuse increa treatm study, addres the ag the go	ed on evaluating various methods of modern communication to use the HCV screening rate in Arizona and link these individuals to ment centers based on their insurance status. With the design of this we can evaluate the most successful method of communication and ss the gaps in linking positive HCV individuals to treatment. Overall, agressive nature of our study is a step in the process to accomplish bal of HCV eradication.
Principal Investi	gator:	[name] & PI
Sub-Investigator	`S:	[name], MS (Physiology), Clinical Research Coordinator, & Sub-I
		[name], FNPC & Sub-I
IRB Number:		Pending
Protocol Date:		Pending

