Email listings of Arizona residents will be obtained from National Data Group and mass emails will be sent through sendgrid.com.

b. Frequency and Resources

Emails will be sent out daily during intervention periods of 2 months followed by a 1month gap for two rounds for each of the different prevalence groups. A project coordinator at the Liver Institute PLLC will assure expectations and targeted numbers are met.

c. Email Content

The email content will follow the template in Appendix 8.1, including an introduction of the program coordinator, introduction to the project as well as brief background information on

the disease and its risk factors (Appendix 8.6). It will also include the steps that need to be taken and contact information to answer any questions.

d. Progress Monitoring

Updates will be obtained from the carrier company as documented proof of the number of emails sent. Information will also be collected on how many emails were rejected and how many were opened. This information will then be used to guide adjustments of upcoming steps if expected response rates are not reached.

2. Direct Text Messages

Response rates to text messages are similar to that of emails at about 2% or 112,136 of the targeted population.

a. Generating Phone List

A list of Arizona residents phone numbers will be generated by National Data Group and messages will be sent to the targeted population through Verizon wireless.

b. Frequency and Resources

Text messaging will similarly follow the protocol described in Figure 3. Messages will be sent daily during the intervention period for 2-month followed by a 1-month gap for two rounds for each of the different prevalence groups.

c. Text Content

The text content will follow the template in Appendix 8.2. The message will be brief in comparison to the email content. It will include an introduction of the program coordinator, introduction to the project, the steps that need to be taken to get screened and a link to more information and background on the disease. It will additionally include contact information to answer any questions or connect to screening and treatment resources.

d. Progress Monitoring

Updates will be obtained from the carrier companies as to how many messages were sent daily and how many were rejected. This information will then be used to guide further changes or alterations if expected response rates are not reached.

Phase 2: Indirect Communication

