1. Newspapers, Advertisement Content, and Duration

Newspaper advertisements are assumed to generate a response rate of 2% or 112,136 of the targeted population. However, according to the local newspaper statistics, the response rate is expected to be higher.

a. Newspapers

The most common local newspaper in Arizona is The Arizona Republic. Both newspapers are well-rounded, published daily or weekly and readily available to the public. This newspaper serves all counties in Arizona, making it efficient and more accessible to all members of the population.

The Arizona Republic – Best Life

According to republic media.com, "Best Life" is the section inside the Arizona Republic dedicated for active, healthy adults and include preventative health tips and postings. This section is published weekly on Mondays and typically generates 46% response rate from the reader population.

The Arizona Republic – Overview

Since the previous section focuses on health-conscious individuals, another post will be published in the overview section, which is distributed daily. According to republicmedia.com, this section reaches 1.1. million adults weekly in the Phoenix area, 32% of local residents. Advertising through the Arizona Republic is therefore likely to generate the expected response rate and reach the majority of our targeted population.

- b. Duration and Monitoring
 - The hepatitis C newspaper advertisement will run similarly to other communication methods during the intervention periods; in 2-month intervals followed by 1-month gap for two rounds for each of the different prevalence groups.
 - Data collection and monitoring will be based on screening numbers during the gap periods. The project coordinator will be responsible for communicating with the magazine to make adjustments as needed.
- c. Advertisement Content
 - The content of the newspaper advertisement will be an infographic designed to present background information on the disease, a brief explanation of the program and its rationale and next steps that need to be taken.
 - The infographic will be designed by the program coordinator to display the information in a simple and clear format to comply with the newspaper's requirements.

2. Social Media

The third approach aimed to target the remaining 33%; 835,414 is social media: including radio and YouTube advertisements. This method is expected to generate a response rate of about 2%.

a. YouTube ➤ Type of Advertisement

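### The synopsis promises to identify the most successful communication method, but the design supports only a descriptive tally by code presented

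*Protocol*

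**What the plan says.** The synopsis, under Results, states: "By comparing diagnostic rates between communication methods, we can identify the most successful method to utilize for a bigger subject outreach". It then adds the proportion linked to care and concludes: "These components taken together will allow us to evaluate the overall success of our study". The synopsis Conclusion repeats that, with this design, "we can evaluate the most successful method of communication".

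The parts of the protocol that decide whether such a ranking is possible are these.

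- **Schedule within a phase (section 3.1).** For email: "Emails will be sent out daily during intervention periods of 2 months", then a one-month gap, for two rounds per tier. For text: "Messages will be sent daily during the intervention period for 2-month followed by a 1-month gap for two rounds". For the newspaper: "in 2-month intervals followed by 1-month gap for two rounds for each of the different prevalence groups". YouTube and radio follow the same pattern as the newspaper.
- **Order across phases (sections 3.1 and 3.3).** Direct messages come first, then media, then shelter and NA/AA visits. The order is identical in the high, medium and low prevalence tiers, and everyone is approached repeatedly.
- **Enrolment (section 4.2).** Each person can enrol once.
- **Attribution (section 3.4).** A time-limited promotion code, specific to the outreach method, is shown at the laboratory. The synopsis says of the code: "This code can be used at the time of receipt or a few months later", as suits the subject.
- **Cycle length in the synopsis.** "Each phase will consist of four cycles of a monthly intervention period in which communication will be active and a two-month gap". This differs from section 3.1.

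**The concern.** To rank methods, each must be tried on comparable people, at comparable times, with outcomes that can be traced to it. The protocol describes none of these. Methods overlap within a phase, follow a fixed order across phases, and partly address different audiences. A difference between codes could therefore reflect a method's place in the sequence, the people it reached, or a message from a co-running method.

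The synopsis offers the comparison as the basis for choosing the method for wider outreach. If the sentences stand, a published ranking could credit or fault a method for reasons unrelated to its effectiveness. Screening more people would not remove the bias.

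**Working it through.** **1. The plan's own figures.** The target population is 5,606,808 (section 3.2), and the tiers sum to it: 391,999 + 4,724,421 + 490,388 = 5,606,808. The expected response is 2% each for email, text and newspaper (section 3.1): 0.02 × 5,606,808 = 112,136, as printed. The plan thus expects these three methods to perform equally.

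**2. Do methods in a phase run together?** Section 3.1 gives 2 rounds × (2 + 1) months = 6 months per tier, and 3 tiers × 6 = 18 months. This fills the Phase 1 windows (Months 1-6, 7-12, 13-18) exactly. Email followed by text would need 2 × 18 = 36 months. On the text they therefore run together, although Figure 3, which the text cites, is not shown. A resident who receives both presents one code, and that code does not say which message led to the test.

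**3. Effect of order.** Assume that response means being screened, which the protocol does not say. Assume also that each method draws 2% independently, with one enrolment per person.

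- A third method yields 0.02 × 0.98² = 1.9208% of the target, or 107,696. Against 112,136 this is a loss of 4,440, or 3.96%.
- A fifth method yields 0.02 × 0.98⁴ of the target, or 103,431, a loss of 7.76%.
- A two-proportion comparison of 2% with 1.9208%, treating the groups as independent, gives z = 9.6 on the full target and z = 2.5 in the smallest tier. Equally effective methods would look significantly different.

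If only a share s of people would ever respond, the response among them is p = 0.02/s and the third method keeps (1 − p)² of its first-use yield:

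| s (assumed) | p | share kept | loss |
|---|---|---|---|
| 100% | 0.02 | 96.0% | 4.0% |
| 50% | 0.04 | 92.2% | 7.8% |
| 10% | 0.20 | 64.0% | 36.0% |

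The documents give no value for s.

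**4. The direction is not fixed either.** Section 3.1 reads newspaper and shelter impact from screening in the gap periods. If a share c of earlier responders is counted in a later period, the later method appears (0.019208 + 0.02c) / (0.02 × (1 − c)) times as productive. That is 1.06 at c = 5%, 1.18 at 10% and 1.80 at 30% (c is assumed). This runs against the loss in step 3.

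**5. Which rate?** Section 5.3 uses diagnosis rate in two senses: 5.2% of tests, expected to stay constant, and a rate per 100,000, expected to rise from 776 to 1,552. The choice matters. In the first case of step 3, at a constant 5.2%, a first method gives 112,136 × 0.052 = 5,831 positives and a third gives 107,696 × 0.052 = 5,600. Per 100,000 of the target that is 104.0 against 99.9, while the positive fraction is 5.2% for both. Depletion alone thus affects numbers screened and diagnoses per population, not positivity.

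**6. Audience.** Radio is placed in programmes for ages 40 and over. Phase 3 goes to shelters and NA/AA meetings. Email and text use separate lists that are not shown to cover the same people (all section 3.1). Positivity can differ on these grounds alone, by an amount the documents do not give.

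**7. Passages that determine overlap.**

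| Item | One place | Another place |
|---|---|---|
| Cycle | Synopsis: 1 month on, 2 off, four cycles = 12 months per phase | Section 3.1: 2 on, 1 off, two rounds = 6 months per tier, 18 per phase |
| Phase 1 | Section 3.1: first nine months | Same sentence: Months 1-18 |
| Phase 2 start | Section 3.1: Month 12 | Phase 1 runs to Month 18 |

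Separately, the newspaper serves all counties and YouTube is limited only to the state. This blurs the prevalence tiers rather than the comparison of methods.

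**The case against.** **The codes are method-specific.** This is the best counter-argument, and part of it stands: tests and positives can be counted by code. The code does not remove co-exposure, depletion or differences in audience.

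**Reach is part of a method's merit.** For choosing an outreach channel, finding more positives in shelters is not purely bias. That is fair, and it is a reason to report such results. It does not make them a ranking of methods on comparable people.

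**Concurrency is inferred, and an analysis plan may exist.** Figure 3 could show something else, so step 2 is conditional. The order and audience problems do not depend on it. No analysis plan can supply an allocation that the design lacks.

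**Code validity is not a flat contradiction.** A time-limited code may still work some months later. The tension is only with the synopsis allowing use whenever the subject is ready.

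**A stronger size is tempting.** Email, text and newspaper at 2% sum to 336,408 (6%), while section 5.3 expects 4% overall (224,272). A reader might infer that one method's whole yield must disappear. The documents do not support this. The 4% is borrowed from breast and cervical cancer campaigns and is not described as a cap on distinct people screened by these three methods. The 8,930 tests per month are a stated minimum, so they set no cap either.

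**Conclusion.** The claim that the study will identify the most successful method is not supported by its design, and the two synopsis sentences should be changed. What the design supports is a descriptive count by code presented.

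The documents do not fix the size or direction of the bias. A loss of about 4% for a third method rests on response meaning screened and on independent 2% responses. It grows if the willing group is small, and late code use can offset or reverse it.

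Two further inferences should be avoided. A reader might think the study's main result is undermined. It is not: the comparison is neither an objective nor an endpoint (sections 2.1 and 2.2), and the measure of 8,930 tests per month (section 5.3) is an overall count. A reader might also think that email versus text escapes the problem because they share a schedule. It does not, since attribution is unresolved and the two lists may reach different people.

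**What to change.** 1. Reword the Results and Conclusion sentences of the synopsis, for example: *Numbers screened and positivity (positives divided by persons screened) will be reported by code presented, prevalence tier and age group. Comparisons across methods and phases are descriptive and do not identify the most successful method.* Demographic and contact data are recorded for each patient (section 3.4), so tier and age group need no new data. Positivity by risk group should not be promised, because section 3.4 collects clinical history only from HCV-positive individuals.
2. Reconcile cycle length between the synopsis and section 3.1, and the Phase 1 and Phase 2 dates within section 3.1. State how long a code stays valid.
3. Describe newspaper and YouTube as statewide exposure when results are shown by tier.

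The cost is wording and one reporting line. Nothing changes in whom the study contacts or how people are screened, beyond settling the schedule that the protocol already needs to settle.

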1.0 Introduction

1.1 Disease Background

CDC statistics from 2013 indicate that deaths due to hepatitis C (HCV) surpassed the number of deaths due to 60 other infectious diseases combined, including HIV and tuberculosis³. HCV is an ever-growing public health issue that continues to be the cause of mortality in millions. Additionally, prevalence of the disease is constantly increasing due to the initial asymptomatic phase and infectious nature of the disease³. Approximately 60-80% of people with the virus will develop chronic HCV infection, characterized by a lifelong illness with serious life-threatening complications such as cirrhosis, and hepatocellular carcinoma¹⁵. The risk of disease progression increases with concurrent heavy alcohol consumption, ingestion of hepatoxic medications or supplements, and presence of poorly managed insulin resistance, iron overload, or other comorbid conditions such as end stage renal disease⁴.

With current effective and well-tolerated antiviral oral therapies, 95% of patients can be effectively treated¹⁵. However, their benefit will be unremarkable if efforts to improve rates of diagnosis and treatment remain the same². Many barriers continue to prevent control and eradication of the disease. These include identifying HCV carriers, connecting to treatment and prevention. Most people infected with the virus are asymptomatic and therefore are unaware of their infection while still being able to transmit it to others. The only way to diagnose the disease in this case is to get tested. Therefore, nationwide screening is required if the future public health burden of hepatitis C is to be ameliorated¹⁶.

1.2 Scientific Rational: Eradication of HCV in Arizona

HCV related malignancies are among the leading causes of mortality in comparison to death from all other causes in Arizona, especially in the middle-age population (Figure 1). The World Health Organization (WHO) set several recommendations with the goal of eradicating HCV by 2030 and several developed countries have taken the initiative to meet these goals¹⁷. The United States on the other hand is significantly lagging to achieve this target. With the current rate of screening, diagnosis, and treatment, it will take several decades to meet the goals of eradication. There is an urgent need to take aggressive action.

LI-HEPC-AZ V1.0 CONFIDENTIAL According to the Institute of Medicine (IOM), 75-90% of HCV positive individuals in the United are unaware of their infection¹⁰. Current HCV standards encourage screening to only those who are thought to be at risk including injection-drug users, baby boomers, persons with known HCV exposure, HIV infection and patients with signs/symptoms of liver disease^{7, 2}. However, these standards leave millions undiagnosed, hence the increasing trends of HCV^{1, 6}. According to the results of the NHANES questionnaire (Figure 2), the primary reason for lack of treatment is lack of diagnosis¹⁶.

For each new acute HCV case that is reported in the United States, the CDC estimates there are approximately 13.9 actual new HCV cases (reported and unreported)¹⁵. This high ratio (total estimated cases to actual reported cases) is primarily a result of the large proportion of individuals with acute HCV who have asymptomatic or minimally symptomatic infection. Therefore, many may continue to transmit the disease to others but find it unnecessary to seek medical care.

1.3 Current Standards: Outreach, Screening, and Therapies

- Currently, there is no standard model of public hepatitis C education and screening promotion. Although approaches like newspaper or media advertisement were used in the past, their benefit remains unknown. On the contrary, there are published reports evaluating the benefit of media campaigns on awareness of breast and cervical cancer screenings. Evaluating the benefit of this project is quite challenging, a meta-analysis revealed short term response of 4% to mass education on improving awareness for mammogram and pelvic examination for breast and cervical cancers, respectively¹⁴. There are no prior studies to estimate the response to HCV screening education in the mass population.
- Current standards encourage HCV screening for individuals considered to be at risk. This includes baby boomers, individuals exposed to infected blood or illicit

drug users. However, these standards do not take into consideration the transmission of disease and other possible causes, leaving millions undiagnosed.

- There are a variety of tests that can detect the presence of Hepatitis C Virus, one of which utilizes anti-HCV ELISA test and is confirmed by HCV PCR. Additional methods include imaging studies and liver biopsies.
- Current standards of treatment include several antiviral medicines that effectively cure the disease in most cases. The course of treatment typically takes 12-24 weeks based on the genotype of disease, extent of liver damage and whether the patient was treated for hepatitis C in the past. In addition to antiviral therapy, complications like cirrhosis and subsequent complications can also be treated using different medical procedures or medicines to prevent risk of liver failure, portal hypertension and liver cancer¹³.
- The Arizona Department of Public Health lags three year on their data compilation and reporting. Most recent data available for review is from 2016.

